6.2. Analyses of Secondary Efficacy Endpoints

6.2.1. Objective Response Rate

Objective response rate (ORR) is defined as the percentage of subjects that achieve a CR or PR as their best response, divided by the total number of subjects available for the analysis within the given population, eg, subjects contained within the ITT Population which is formed of all subjects enrolled into the study, the Safety Population which is formed of all subjects receiving at least 1 dose of pomalidomide as outlined within [Section 5](#) of this SAP, and the Response Population which is formed of all subjects completing at least one cycle of study therapy if having not discontinued since the first dose due to either disease progression or relapse and having satisfied the study inclusion and exclusion criteria. The corresponding 2-sided, 95% Clopper-Pearson CI will also be provided.

Disease assessments recorded on or after start of a new anticancer therapy will not be considered, nor will disease assessments reported after a PD has been observed.

In addition, best overall response will be summarized by number and percentage of a subject's best response that meets one of the following categories: (ordered from best response to worst response) CR, PR, SD, PD, or not evaluable. The number of subjects achieving a SD as their best response will also be sub-categorized by the number of subjects with a SD maintained for at ≥ 6 cycles (≥ 3 cycles for the DIPG tumor type/disease indication).

6.2.2. Long-term Stable Disease Rate

Long-term SD rate is defined as the percentage of subjects that achieve a SD maintained for ≥ 6 cycles (≥ 3 cycles for the DIPG tumor type/disease indication), divided by the total number of subjects available for the analysis within the given population, eg, subjects contained within the ITT Population which is formed of all subjects enrolled into the study, the Safety Population which is formed of all subjects receiving at least 1 dose of pomalidomide as outlined within [Section 5](#) of this SAP, and the Response Population which is formed of all subjects completing at least one cycle of study therapy if having not discontinued since the first dose due to either disease progression or relapse and having satisfied the study inclusion and exclusion criteria. The corresponding 2-sided, 95% Clopper-Pearson CI will also be provided.

Calculation of stable disease duration starts at the time of first dose of pomalidomide and continues until the date of the first observation of PD is recorded or death due to any cause, regardless of whether the subject achieves a CR and/or PR within that period, or until the date of the last disease assessment if no PD or death is recorded; if the difference is ≥ 6 cycles (≥ 3 cycles for the DIPG tumor type/disease indication), ie, the subject has not had a documented PD before Cycle 7, Day 1 (Cycle 4, Day 1 for the DIPG tumor type/disease indication) and has completed 6 cycles of pomalidomide (3 cycles for the DIPG tumor type/disease indication), then the SD will be considered as being maintained for ≥ 6 cycles (≥ 3 cycles for the DIPG tumor type/disease indication).

For identification of PD for this endpoint, PD is classified as a PD as observed during a response assessment (both during the Treatment Period and the Follow-up Period if applicable); the first time this occurrence is observed is selected as the PD date.

Disease assessments recorded on or after start of a new anticancer therapy will not be considered, nor will disease assessments reported after a PD has been observed.

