6.4.1.7. Overall Response Assessment

The overall response assessment takes into account response in both target and non-target lesions, the appearance of new lesions, current corticosteroid use (compared to screening/baseline) and neurologic symptoms/examination (clinical status) according to the criteria described in [Appendix C](#).

Subjects who do not meet the criteria for an objective response or disease progression by the end of Cycle 6 (end of Cycle 3 for DIPG subjects) will be considered as having long-term SD.

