9.6. Efficacy Analysis

Objective Response and Long-term Stable Disease Rate

Objective response and long-term SD rate (ORSDR), is defined as the total number of subjects achieving either an OR (either CR or PR) within the first 6 cycles of treatment (within 3 cycles for DIPG) or a long-term SD (SD maintained for ≥ 6 cycles [≥ 3 cycles for DIPG]), over the total number of subjects evaluable for analysis. Evaluable is defined as a subject completing at least one cycle of study therapy or discontinuing treatment earlier due to a PD. Subjects completing at least one cycle of study therapy but not having at least one subsequent (post-baseline) disease assessment will be considered a non-responder. The corresponding Clopper Pearson 95% confidence interval (CI) shall be calculated for each rate per stratum. Each stratum will be analyzed separately. Analysis of this endpoint will be based on the Response Population, with secondary analyses based on the ITT Population and/or Safety Population.

Objective Response Rate

The ORR is defined as the total number of subjects achieving an OR (either CR or PR), over the total number of subjects evaluable for the analysis. Disease responses occurring after start of a new anticancer therapy shall not be considered. Each stratum will be analyzed separately. Analysis of this endpoint will be based on the ITT Population and/or Safety Population.

Long-term Stable Disease Rate

The long-term SD rate is the proportion of subjects achieving long-term SD, defined as a SD maintained for ≥ 6 cycles (≥ 3 cycles for DIPG), over the total number of subjects evaluable for the analysis. The corresponding Clopper Pearson 95% CI shall be calculated for each rate per stratum. Each stratum shall be analyzed separately. Analysis of this endpoint will be based on the ITT Population and/or Safety Population.

Duration of Response

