Appendix B: Tumor Response Categories for Target and Non-target Lesions

Target Lesions

For the purpose of this study, response criteria for target lesions are defined as follows:

- **Complete Response (CR):**
 - Complete disappearance on MRI of all measurable lesions.
- **Partial Response (PR):**
 - A reduction of $\geq 50\%$ in tumor size by bi-dimensional measurement (taking as reference the baseline measurements) quantified by the sum of the products of the perpendicular diameters of measurable lesions.
- **Stable Disease (SD):**
 - A decrease of $< 50\%$ or an increase of $< 25\%$ in the sum of the products of the perpendicular diameters of measurable lesions and no evidence of new lesions. Response does not meet the criteria for CR, PR or PD.
- **Progressive Disease (PD):**
 - $\geq 25\%$ increase in the bi-dimensional measurement as quantified by the sum of the products of the largest diameters of the measurable lesions taking as a reference the smallest disease measurement recorded since the start of protocol therapy (nadir).

Non-target Lesions

For the purpose of this study, response criteria for non-target lesions are defined as follows:

- **Complete Response (CR):**
 - Disappearance of all non-target lesions.
 - If spine MRI and/or lumbar CSF cytology were previously positive, it must be negative at time of assessment.
- **Incomplete Response/Stable Disease (IR/SD):**
 - The persistence of non-target lesions, stable (no progression) or decrease in size.
 - If spine MRI and/or lumbar CSF cytology were previously positive at baseline and remains positive with no other evidence of PD.
- **Progressive Disease (PD):**
 - The appearance of one or more new lesions and/or unequivocal progression of existing non-target lesions.
 - If spine MRI and/or lumbar CSF cytology were previously negative and became positive.

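### SAP 6.2.2 lets a responder who completes 6 cycles (3 for DIPG) without progression also count as long-term stable disease, contrary to the protocol's definition

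*SAP*

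**What the plan says.** **Protocol.** Section 6.4.1.7, repeated in Appendix C and the Protocol Summary, assigns long-term SD by exclusion: "Subjects who do not meet the criteria for an objective response or disease progression by the end of Cycle 6" (Cycle 3 for DIPG). Appendix B defines SD on target lesions the same way: "Response does not meet the criteria for CR, PR or PD". Section 9.6 builds the secondary endpoint on that category: "The long-term SD rate is the proportion of subjects achieving long-term SD, defined as a SD maintained for ≥ 6 cycles" (3 for DIPG).

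**SAP 6.2.2.** The numerator reads "Long-term SD rate is defined as the percentage of subjects that achieve a SD maintained for ≥ 6 cycles" (3 for DIPG). SD duration runs from first dose to progression, death or, failing both, the last assessment, "regardless of whether the subject achieves a CR and/or PR within that period". SD counts as maintained if "the subject has not had a documented PD before Cycle 7, Day 1" (Cycle 4 Day 1 for DIPG) and 6 (3) cycles of pomalidomide were completed. Nothing requires that the subject had no response.

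**SAP 6.2.1.** Here the wording is tied to best response: "Objective response rate (ORR) is defined as the percentage of subjects that achieve a CR or PR as their best response". The same section plans a best-overall-response table in which "The number of subjects achieving a SD as their best response will also be sub-categorized" by whether SD lasted 6 (3) cycles.

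**SAP 6.1.1.** The primary endpoint (ORSDR) uses the same SD clock, but with a best-response limit and as an either/or count.

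**The concern.** Under the protocol, a response by the end of Cycle 6 (3) takes a subject out of long-term SD. Under SAP 6.2.2 it does not. What 6.2.2 measures is closer to the proportion progression-free with 6 (3) cycles completed, reported under the name of stable disease.

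The best-response limit cannot be read into 6.2.2 by implication. A subject whose best response is SD has no CR or PR, so a clause about an intervening CR or PR could affect only responders. In 6.1.1 the clause does no harm, because the composite counts each subject once. In 6.2.2, without the limit, it changes the endpoint.

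Two things follow. The reported secondary rate may not be the one the protocol defines. And one report may carry two different long-term SD counts for the same population, one from 6.2.2 and one from the 6.2.1 table.

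**Working it through.** **1. The plan's own figures.** Neither document gives an expected long-term SD rate, so there is none to reproduce. The design does reproduce (Protocol 9.3; SAP 6.5). With rates of 10% and 40%, at least 2 of 9 to continue and at least 5 of 20 to succeed:

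P(success) = Σ over x = 2 to 9 of P(X₁ = x; 9, p) × P(X₂ ≥ 5 − x; 11, p)

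This gives 0.035 at p = 0.10 and 0.902 at p = 0.40, as planned (5% and 90%). Neither figure depends on the rule at issue, because a responder is already a success.

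**2. Who is counted where.** For one stratum with n subjects, let:

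- S = best response SD, with 6 (3) cycles completed and no progression before the landmark;
- k = SD, then CR or PR by the end of Cycle 6 (3), with 6 (3) cycles completed and no progression before the landmark;
- L = SD through the landmark, with a first response later;
- e = other responders (progressed or stopped before completing 6 (3) cycles).

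Then:

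- long-term SD, SAP 6.2.2 = (S + k + L)/n
- long-term SD, Protocol 6.4.1.7 = (S + L)/n
- SD row of the 6.2.1 table = S/n
- ORR = (k + L + e)/n
- ORSDR = (S + k + L + e)/n

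So SAP minus protocol = k/n; SAP 6.2.2 minus the 6.2.1 row = (k + L)/n; and ORR plus the SAP long-term SD rate exceeds ORSDR by (k + L)/n.

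**3. Numbers.** The documents give no expected split between response and SD, so k is an assumption shown over its range. Take n = 20, ORSDR at the success threshold of 5/20, and L = e = 0. Intervals are the planned Clopper-Pearson 95%.

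| k | SAP 6.2.2 | Protocol rule (95% CI) | ORR + SAP long-term SD |
|---|---|---|---|
| 0 | 25% | 25% (8.7–49.1) | 25% |
| 1 | 25% | 20% (5.7–43.7) | 30% |
| 2 | 25% | 15% (3.2–37.9) | 35% |
| 3 | 25% | 10% (1.2–31.7) | 40% |
| 4 | 25% | 5% (0.1–24.9) | 45% |
| 5 | 25% | 0% (0–16.8) | 50% |

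The SAP interval is 8.7–49.1% throughout. At ORSDR 8/20 the SAP rate is 40%, against 30% under the protocol rule for k = 2 and 20% for k = 4. In a stratum closed after Stage 1 (n = 9), one such subject is 1/9 = 11.1 points.

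**4. Where the wording is unclear.** A subject whose first post-baseline scan already shows CR or PR never records SD, so may not meet the opening words of 6.2.2, yet passes its duration test. This matters most for DIPG. The first scheduled scan there is Cycle 4 Day 1 (Protocol 3.1 and 6.4.1), which is the landmark itself, so on scheduled scans no DIPG subject can record SD and then respond before it.

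**The case against.** Four points on the other side have force.

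- **The split is available elsewhere.** A reader might infer that the report could not show how much of a positive result is stabilisation and how much is shrinkage. The documents do not support that: the 6.2.1 table lists CR, PR and SD, with SD divided at 6 (3) cycles. What remains is a mislabelled rate beside a table that may disagree with it.
- **Not every responder is caught.** A reader might infer that any responder progression-free at the landmark is counted. SAP 6.2.2 also requires 6 (3) completed cycles, so a responder who stops early is left out, and it requires that SD was achieved.
- **No partition is promised.** A reader might infer that ORR and long-term SD were designed to add up to ORSDR. Neither document says so. Protocol Table 2 gives them different time frames, with ORR running to the end of follow-up, and a late responder falls in both even under the protocol's rule.
- **The effect may be small.** The only paediatric response counts in the documents are for lenalidomide (Protocol 1.3.1): 2 partial responses among 44 evaluable subjects in one study and none in the other. At 2/44, 20 subjects yield 20 × 2/44 = 0.9 responders, and the binomial chance of 3 or more is about 6%. That suggests a gap of about 0 to 5 points. It is weak guidance: it concerns a different drug, and both responses were in a pilocytic astrocytoma and an optic pathway glioma, not in this trial's strata.

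All four limit the consequence. None removes the conflict between SAP 6.2.2 and Protocol 6.4.1.7, or between SAP 6.2.2 and SAP 6.2.1.

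**Conclusion.** The inconsistency stands and is worth correcting, as a definition problem in one secondary endpoint. The text is clear for SD followed by CR or PR, and ambiguous when the first scan is already a response. The excess over the protocol's rate is k/n: never negative, zero if no responder qualifies, 5 points per subject at n = 20. Its realised size rests on k, which the documents do not let anyone predict, so it would be wrong to say that the reported rate will be inflated.

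A reader might also infer that the primary result or a go/no-go decision is at risk, or that subjects are counted twice within a rate. Neither follows. ORSDR counts each subject once, the rules of at least 2 of 9 and at least 5 of 20 are unchanged, and the overlap is one subject appearing in two separate secondary rates.

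**What to change.** In SAP 6.2.2:

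1. Delete the clause that disregards an intervening CR or PR, and restrict the numerator to subjects with no CR or PR by the end of Cycle 6 (Cycle 3 for DIPG), as in Protocol 6.4.1.7. Keep the existing conditions on progression and completed cycles.
2. State that the scan scheduled for Cycle 7 Day 1 (Cycle 4 Day 1 for DIPG), which may be done up to 7 days early, settles response status at the landmark. Otherwise the DIPG stratum has no scheduled post-baseline scan on which to apply the rule.
3. Say how the rate relates to the SD row of the 6.2.1 table. After the change they differ only by late responders (L above), who are long-term SD under the protocol but do not have SD as best response. Restricting 6.2.2 to SD as best response would match the table but drop those subjects, so it is not the protocol's definition.
4. If the present quantity is wanted, report it separately as the proportion progression-free with 6 (3) cycles completed.

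The cost is SAP wording and a small programming change. No new data are needed, and the design and primary analysis stay as they are.

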6.2.3. Duration of Response

Duration of response (DoR) will be presented in weeks is defined as the duration from initial response (either a CR or PR) to documented PD or death due to any cause, whichever occurs first. The response criteria should be defined in the protocol prior to the start of the study. Duration of response for subjects last known to be alive without PD is censored at the date of last adequate response assessment, or at the start of a new anticancer therapy, whichever occurs first.

The underlying analysis population is confined to those who have responded.

For identification of PD for this endpoint, PD is classified as either a PD as observed during a response assessments (both during the Treatment Period and the Follow-up Period if applicable), or as a PD as recorded on the treatment discontinuation and/or the study discontinuation eCRF; the first time this occurrence is observed is selected as the PD date.

Duration of response will be summarized by median DoR time, along with the corresponding 95% CI, calculated using Kaplan-Meier methods (the estimate of variance will be calculated using Greenwood's formula) ([Kaplan and Meier, 1958](#)) for each tumor type/disease indication separately. The Kaplan-Meier curve for DoR will be presented graphically. The proportion remaining progression/death free at 3, 6, 9, 12, 18, and 24 months will be reported and the corresponding standard error provided.

Due to the low anticipated number of subjects and events/censoring, additional summary statistics will be provided, including the arithmetic mean, median, standard deviation (StdDev), first quartile (Q1), third quartile (Q3), minimum (Min), and maximum (Max) values.

Disease assessments recorded on or after start of a new anticancer therapy will not be considered, nor will disease assessments reported after a PD has been observed.

6.2.4. Progression-free Survival

Progression-free survival (PFS) will be presented in weeks and is defined as the time from the date of first pomalidomide dose until the date a PD is first observed or date of death (any cause), whichever occurs first. Subjects who do not have a PD or have not died at the time of an analysis will be censored at the time of their last disease assessment or at the time of start of new anticancer therapy, whichever occurs first.

For the purpose of identification of a PD for this endpoint, PD is classified as either a PD as observed during a response assessments (both during the Treatment Period and the Follow-up Period if applicable), or as a PD as recorded on the Disposition – Treatment and/or the Disposition – Follow-up eCRF; the first time this occurrence is observed is selected as the PD date.

Progression-free survival will be summarized by median progression-free time along with the corresponding 95% CI, calculated using Kaplan-Meier methods (the estimate of variance will be calculated using Greenwood's formula) ([Kaplan and Meier, 1958](#)) for each tumor type/disease indication separately. The Kaplan-Meier curves for PFS will be presented graphically. The number and percentage of total disease progression/deaths, as identified for PFS events will be summarized. The proportion remaining progression/death free at 3, 6, 9, 12, 18, and 24 months will be reported and the corresponding standard error provided.

Due to the low anticipated number of subjects and events/censoring, additional summary statistics will be provided, including the arithmetic mean, median, StdDev, Q1, Q3, Min, and Max values.

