6.4.1.8. Independent Central Response Review

Response evaluations will be based on MRI results obtained at each site and will be assessed locally and by an independent central reviewer. Corticosteroid use and clinical assessments (ie, neurologic status) will also be considered when determining overall response. The local Investigator’s assessment will be used for subject eligibility and treatment decisions. Efficacy based endpoints incorporating tumor assessments (primary and secondary) will be based on the independent central assessment.

Imaging/response data will be centrally collected and checked for quality by an imaging contract research organization (CRO) designated by Celgene. Independent central review (screening/

baseline and post-baseline assessments) will be performed for all MRIs collected for response assessment. Further details regarding MRI acquisition requirements and image submission procedures are outlined in the Imaging Manual.

Details of the central review process and requirements for central imaging review will be described in the independent review charter. Results of the central review will not be provided to the sites.

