6. STATISTICAL METHODOLOGY FOR EFFICACY

Tables will be provided to describe the efficacy endpoints for the Response Population, Safety Population and ITT Population; the ITT Population will only be invoked if at least one of the subjects enrolled does not receive a single dose of pomalidomide. In addition, analysis of the primary endpoint, ORSDR, will be based primarily on the Response Population and decision making such as go/no-go into stage 2 will be based on the analysis using this analysis population. Tables will present data by tumor type/disease indication separately and not in aggregate. Listings will display response assessment data for the ITT Population.

Efficacy endpoints reliant on disease assessments will be based on the independent central response assessments.

In instances where disease assessments are reliant on measurements being collected over a series of days, the last day a measurement is recorded will be used as the date for documentation of the CR, PR, SD or PD.

Missing efficacy data will not be imputed.

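### SAP 6.2.3 and 6.2.4 also count progression recorded on disposition forms, earliest date winning, although both documents base tumor endpoints on central review without exception

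*SAP*

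**What the plan says.** **The general rule.** Protocol 6.4.1.8 states: "Efficacy based endpoints incorporating tumor assessments (primary and secondary) will be based on the independent central assessment". The Protocol Summary and Protocol 6.4.1 repeat it. SAP 6 agrees: "Efficacy endpoints reliant on disease assessments will be based on the independent central response assessments". None of these places excepts PFS or DoR.

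**The PFS and DoR definitions.** SAP 6.2.4 accepts progression at a response assessment "or as a PD as recorded on the Disposition" forms for treatment or follow-up, and "the first time this occurrence is observed is selected as the PD date". SAP 6.2.3 accepts progression at a response assessment "or as a PD as recorded on the treatment discontinuation and/or the study discontinuation eCRF", with the same first-occurrence rule. Protocol 9.6 defines both endpoints without mentioning any form.

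**The contrast.** For stable-disease duration, SAP 6.1.1 (ORSDR) and 6.2.2 (long-term SD rate) use progression at a response assessment only.

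**The concern.** A form entry of progressive disease is the site's judgement. Letting it set the event date in two secondary endpoints departs from the central-review rule in both documents. A reader of the study report would take PFS and DoR to be centrally reviewed when some events may rest on a local call that central review never confirmed. DoR is the plainest case: its start must be a central response, while its end may be a local progression, so one interval is measured by two standards.

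**Working it through.** No figure in the plan is at issue, so the check is mainly a comparison of text.

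**1. Can a form progression reflect central review?**
- Protocol 6.4.1.8 says central results are not provided to sites.
- The same section says the local investigator's "assessment will be used for subject eligibility and treatment decisions".
- Protocol 11.1 makes stopping treatment the treating physician's responsibility.
- SAP 7 lists progressive disease among the reasons collected on the Disposition – Treatment and Disposition – Follow-up forms.

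The SAP does not call these investigator forms, but a progression entered there cannot have come from central review.

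**2. Direction.** Let C be the central progression date and F the form date. The SAP uses min(C, F).
- If F is on or after C, nothing changes.
- If F precedes C, the event moves earlier.
- If there is no C, a subject otherwise censored (or counted later at death) becomes an event at F.

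No case moves progression later.

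**3. Which case matters most?** Progression ends treatment (Protocol 3.1). The end-of-treatment MRI is done only when the reason for stopping is not progression (Protocol 6.2.1; Table 4, footnote j). Off-treatment MRIs are scheduled only for subjects who stop before progression (Protocol 6.3.3). After a local progression that central review does not confirm, no later scan is scheduled that could supply C. The main contrast is therefore event versus censoring, not a shift by a set interval.

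**4. Size per subject for PFS.** With no earlier censoring, each Kaplan-Meier event lowers the curve by 1/n. For a stratum of 20 this is 1/20 = 5.0 percentage points; for 9 it is 1/9 = 11.1. A subject censored instead causes no step, so one form-only progression changes the curve by about 5 to 11 points at that time. DoR includes responders only, so the step is 1/R, with R the unknown number of responders; the 5 to 11 range does not carry over.

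**5. Size if some dates do shift.** This illustration covers only the less common case where a later central progression exists. Assumptions, none from the documents:
- time to progression is exponential with median m = 8, 12 or 26 weeks;
- progression is read at the next scheduled non-DIPG scan, which after week 24 (Cycle 7 Day 1) is week 36 (Cycle 10 Day 1);
- a fraction q = 10% to 30% have local progression one scheduled scan before central.

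With S(t) = 0.5^(t/m), the proportion progression-free beyond week 24 is S(24) under central review and S(24) − q[S(24) − S(36)] under the earliest-date rule.
- m = 8: S(24) = 0.125, S(36) = 0.044; 12.5% becomes 11.7% (q = 10%) to 10.1% (q = 30%).
- m = 12: S(24) = 0.250, S(36) = 0.125; 25.0% becomes 23.8% to 21.3%.
- m = 26: S(24) = 0.527, S(36) = 0.383; 52.7% becomes 51.3% to 48.4%.

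The fall is about 0.8 to 4.3 percentage points under these assumptions.

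**6. Overlap with ORSDR.** Long-term SD requires no documented progression before Cycle 7 Day 1 (Cycle 4 Day 1 for DIPG) and also completion of 6 (3) cycles of pomalidomide (SAP 6.1.1, 6.2.2). A subject taken off for local progression earlier fails the second condition whatever central review says. A conflict remains mainly where the scan allowed in the 7 days before Cycle 7 (4) Day 1 is called progression locally and stable centrally, after the required cycles are complete.

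**The case against.** The strongest defence is clinical progression. Protocol Table 10 lets neurologic decline alone establish progression, and Protocol 6.4.1.5 leaves its definition to the investigator. Decline between scans may be recorded only on a disposition form; a central-only rule would then censor that child at the last assessment, probably informatively. Counting such events can only shorten PFS and DoR, so it does not flatter the drug. The two SAP definitions are also explicit enough to program.

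The risk of informative censoring stands, and is why an either-source analysis is needed. The rest does not remove the conflict. SAP 6.2.3 and 6.2.4 do not limit form progression to clinical decline, and Protocol 6.4.1.8 already has clinical status and corticosteroid use considered in overall response. How the central reviewer receives those data is left to a charter not available here.

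Four stronger readings are tempting but not supported:
- *That PFS and DoR rest on the forms alone.* Response-assessment progression is named first; the form is an added source.
- *That each discordant subject moves by at least one scan interval (8 or 12 weeks).* MRIs may be done whenever clinically indicated (Protocol 3.1), and within 72 hours for subjects on steroids needing an increase for worsening neurologic symptoms (Protocol 8.1.2). Dates may differ by days, and often no later scan is scheduled.
- *That PFS broadly contradicts the primary endpoint.* The completed-cycles condition confines this to a narrow window.
- *That form dates are not scan dates.* The form's date fields are not shown, and SAP Appendix A2, section 1, gives the date of the determining tumor scan as its example of a progression date.

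**Conclusion.** The conflict is real for both PFS and DoR: the SAP's endpoint definitions admit a local source that its own general rule and the protocol's exclude. The direction is certain, since the rule can only bring progression forward or add events. The total effect is unknown because no discordance rate is given. For PFS, each subject switched from censored to event is worth about 5 to 11 percentage points at that time, assuming 9 to 20 subjects and no earlier censoring; for DoR it depends on the number of responders. A reader might infer that the Stage 1 or final decision is at risk. It is not: that decision uses ORSDR, and PFS and DoR are secondary and descriptive, with no hypothesis test. What is at stake is the value and the labelling of two secondary estimates.

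**What to change.** In SAP 6.2.3 and 6.2.4, define progression for the main analysis as progression on the independent central overall response assessment (which is to take clinical status and corticosteroids into account), or death. Prespecify one sensitivity analysis using the earliest progression from either source, and tabulate events as central, local form only, or death.

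If the sponsor intends the forms to capture clinical progression, the alternative is to state that exception in SAP 6 and the protocol, limit form progression to it, label both endpoints as mixed-source, and report the central-only version alongside.

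Cost: SAP wording and one extra table per endpoint, plus protocol wording for the alternative. The drawback is that some locally called progressions are censored in the central-only analysis, possibly informatively; the either-source analysis shows how much that matters.
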